3.9.5 Immunology Assessments

Immunological evaluations will include Panel Reactive Antibodies (PRA) with HLA class I and II screening and testing for allelic reactivity at Day 1, Week 4 and Week 12. The number (%) of subjects that are HLA Class I and II positive will be provided for each visit.

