- Treatments used for all other burn areas following excision and %TBSA treated with each (other than StrataGraft treatment sites)
- Number of OR procedures required for burn treatment: excisions, application of StrataGraft tissue and all other grafting procedures, including autografts, allografts, and xenografts
- Duration of each OR procedure
- Length of hospital stay
- Prescription drugs given at discharge from the hospital for wound-related events including pain control, itch, psychotropics, and antibiotics
- Re-admission within 30 days after discharge
- Whether a re-admission is planned
- Length of hospital stay of re-admission

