8.3. Concomitant Procedures

Any concomitant procedure (including transfusions, use of xenogenic or allogeneic products, negative pressure wound therapy, etc.) must be recorded in the eCRF after the consent form is signed and throughout the duration of the study.

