8.4. Randomization and Blinding

This study is designed as an open-label, single arm study in which all subjects receive StrataGraft skin tissue and all other burn wounds will be treated per institutional SoC. No randomization will be conducted, and no blinding is required for the study.

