Protocol Section/Issue/Rationale for Change	Removed Text Displayed in Strikethrough Font	New Text Bolded

{not formerly included}
 
Consent for registry added as separate entry/
 
Rationale:
 
For clarification for when collection of consent for the registry is possible: presented as separate entry from initial informed consent and clarified time points for collection
 
{Immunology testing added}/
 
Rationale:
 
Serves to supplement the PRA data in the StrataGraft clinical development program, by providing additional HLA I and II findings associated with the use of StrataGraft skin tissue.
		
Consent for direct contact by Sponsor and safety registry post study
 
Section 16.3 Written Informed Consent
 
Consent must also be obtained for direct contact by Sponsor for the post study safety registry during the study period.
 
Section 12.2.3 Immunology
 
Blood collection for PRA testing (HLA I and II) at Day 1 (Baseline), Week 4, and Week 12.
 
Section 12.3.5.3 Immunology Assessments
 
Immunological evaluations will include PRA with HLA class I and II screening and testing for allelic reactivity.

Protocol Section/Issue/Rationale for Change	Removed Text Displayed in Strikethrough Font	New Text Bolded						

{Visit windows expanded by adding footnotes to the Schedule of Assessments table}/
 
Rationale:
 
Increases assessment windows in case of publicly stated emergencies.
		
a In public state of emergency situations, the Weeks 1 and 2 visit windows can be expanded to include \pm 5 days.
 
b In public state of emergency situations, the Week 4 visit window can be expanded to include \pm 12 days.
 
c In public state of emergency situations, the Weeks 8, 12, and 24 visit windows can be expanded to include \pm 14 days.
						

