
Section 12.2.4 Regrafting and Delayed Wound Healing
 
{not formerly included}/
		
Section 12.2.4 Regrafting and Delayed Wound Healing
 
In the event that a StrataGraft treated area needs to be regrafted with either an autograft or a xenograft after treatment

Protocol Section/Issue/Rationale for Change	Removed Text Displayed in Strikethrough Font	New Text Bolded

Rationale:
 
Graft failure is not an adverse event as it is a failure of efficacy (defined as reepithelialization) rather than being a safety concern.
		
with StrataGraft skin tissue, the event would not be marked as an AE, but rather as a treatment failure. In the event that there is an accompanying wound degradation event occurring simultaneously such as infection that results in delayed wound healing, the delayed wound healing secondary to the ongoing infection can be listed as an AE or SAE as applicable. If that infective process eventually warrants a regrafting, the regrafting should still be marked as a treatment failure and not an AE.

Section 12.2.3 Immunology {not formerly included}/
 
Rationale:
 
Serves to supplement the PRA data in the StrataGraft Clinical Development program, by additionally providing HLA I and II findings associated with the use of StrataGraft skin tissue.
		
Section 12.2.3 Immunology
 
Blood collection for PRA testing (HLA I and II) will be conducted at Day 1 (Baseline), Week 4, and Week 12.

Section 12.3.5.4 Pregnancy Testing
 
A urine pregnancy test for women of child-bearing potential will be performed at Screening and all positive urine tests will be confirmed with a serum pregnancy test.
	
Section 12.3.5.4 Pregnancy Testing
 
A urine pregnancy test for women of child-bearing potential will be performed at Screening and all positive urine tests will be confirmed with a serum pregnancy test.
	
Section 12.3.5.4 Pregnancy Testing
 
A serum pregnancy test for women of child-bearing potential will be performed at Screening using the local laboratory.
 
Should a pregnancy be confirmed after

Protocol Section/Issue/Rationale for Change	Removed Text Displayed in Strikethrough Font	New Text Bolded

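### The only planned HLA antibody summary is a crude percentage positive per visit, which cannot separate StrataGraft-related antibody from transfusion- or allograft-related antibody

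*SAP*

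**What the plan says.** **Tests and output.** SAP 3.9.5: "Immunological evaluations will include Panel Reactive Antibodies (PRA) with HLA class I and II screening and testing for allelic reactivity at Day 1, Week 4", then again at Week 12. Protocol 12.2.3 and 12.3.5.3 give the same tests and times. The SAP then plans one output, the number and percentage of subjects positive for HLA class I and II at each visit. It does not say whether that means each class or both together. It plans no count of conversions from a negative Day 1 result and no summary of allelic reactivity.

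**Purpose.** The Amendment 1 rationale (Protocol Appendix 1) says the testing supplements the programme's PRA data by "providing additional HLA I and II findings associated with the use of StrataGraft skin tissue". This is the only purpose given, and nothing in the current text contradicts it.

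**Design.** Protocol 8.4: "all subjects receive StrataGraft skin tissue and all other burn wounds will be treated per institutional SoC". There is no comparator.

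**Other sources of foreign HLA.** Protocol 8.3: "Any concomitant procedure (including transfusions, use of xenogenic or allogeneic products, negative pressure wound therapy, etc.) must be recorded in the eCRF". Recording starts at consent, and the section sets no restriction. Protocol section 4 names allograft as an option for excised areas when autograft is not available. The resource-use endpoints in Protocol 6.1 count "all other grafting procedures, including autografts, allografts, and xenografts". SAP 3.8.2 counts allograft among regrafting procedures on StrataGraft sites.

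**Links between the two.** SAP 3.6 summarises concomitant procedures by location and overall. SAP 3.8.3 applies subgroups to wound closure and TEAE endpoints only. Neither connects exposure to HLA results.

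**The concern.** Blood products and human allograft carry HLA from people other than the two StrataGraft cell donors. They can be given within the same Day 1 to Week 12 window in which the antibody samples are drawn. In a single-arm study no untreated group shows how much antibody would have appeared without the product, so separation has to come from within the treated subjects. The plan collects information that could help (exposure records and allelic reactivity) but uses neither in the immunology summary.

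Two errors are possible. Antibody caused by transfusion or allograft could be taken for a product effect. Conversely, a product effect could be dismissed as due to transfusion, because the table offers no less confounded group in which to look. Antibody already present at Day 1 also enters every later visit's percentage. Immunological changes are listed among the safety assessments in the synopsis, and safety is the study's primary objective, although HLA positivity is not itself an endpoint.

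**Working it through.** The documents give no expected HLA rate, exposure rate or precision target, so there is no figure of the plan's own to reproduce. The check asks whether the planned output can distinguish the competing explanations.

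**Inputs from the documents:** single arm; about 100 subjects; samples at Day 1, Week 4 and Week 12; crude percentage positive per visit.

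**Inputs assumed, for illustration only:**
- b = proportion positive at Day 1, 5% to 15%
- q = proportion sensitised by the product, 0% or 10%
- f = proportion transfused or allografted, 20% to 50%
- s = proportion of those sensitised by that exposure, 10% to 50%, plus 0% for the product-only case

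The two routes are taken as independent, and antibody present at Day 1 is taken to persist.

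**Formulas**
- Newly positive = 1 − (1 − q)(1 − f·s)
- Positive at a visit = b + (1 − b) × newly positive

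**Step 1. Different causes, same result.**
- Product only (q = 0.10, s = 0): 1 − 0.90 × 1 = 10%
- Other exposure only (q = 0, f = 0.50, s = 0.20): 1 − 1 × 0.90 = 10%
- Other exposure only (q = 0, f = 0.20, s = 0.50): 1 − 1 × 0.90 = 10%

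For any given b the planned visit percentage is identical in all three.

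**Step 2. Visit percentage with no product effect (q = 0).**
- Low end (b = 0.05, f = 0.20, s = 0.10): 0.05 + 0.95 × 0.02 = 6.9%
- High end (b = 0.15, f = 0.50, s = 0.50): 0.15 + 0.85 × 0.25 = about 36%

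**Step 3. What a split among Day 1 negative subjects would show.**

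| Scenario | New, unexposed | New, exposed |
|---|---|---|
| q = 0.10, s = 0 | 10% | 10% |
| q = 0, f = 0.50, s = 0.20 | 0% | 20% |
| q = 0, f = 0.20, s = 0.50 | 0% | 50% |

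The three scenarios now differ.

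**Step 4. Precision left in the unexposed stratum.** If none of n unexposed subjects converts, the exact upper 95% limit is 1 − 0.025^(1/n).
- With 100 subjects all negative at Day 1, n = 80 gives 4.5% and n = 50 gives 7.1%.
- Removing Day 1 positives, b = 0.05 and f = 0.20 leaves 0.95 × 0.80 × 100 = 76, limit 4.7%.
- b = 0.15 and f = 0.50 leaves 0.85 × 0.50 × 100 = 42.5; with n = 42 the limit is 8.4%.

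The stratum stays informative, but only loosely.

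**The case against.** The strongest reply is that SAP 3.8 makes every analysis descriptive, that HLA results are not an endpoint, and that the SAP makes no causal statement about them. Protocol 13.3 promises listings of all eCRF and laboratory data, and SAP 3.6 summarises the procedures. With about 100 subjects, someone could therefore check each positive against its exposure record. The table shells and programming specifications are separate documents and may contain more.

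Much of that is correct, but it does not remove the point. A check of listings after the results are seen does not fix in advance who counts as exposed or what the denominator is. The shells should implement an analysis that the SAP defines. The proposed change is itself only descriptive.

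Several stronger readings are tempting, and the documents do not support them:
- **A reader might infer that transfusion is expected in this study.** Protocol 8.3 requires recording only, and how often it will occur is not stated. That transfusion is unrestricted is inferred from the absence of any limit.
- **A reader might infer that any rise will be reported as caused by StrataGraft.** The wording about association stands in the amendment rationale, not in the analysis text.
- **A reader might infer that a trend of HLA positivity with treated area will mislead.** No such analysis is planned.
- **A reader might infer that unexposed subjects alone give the product's effect.** Recording starts at consent, so earlier transfusions may be missed. The stratum also probably under-represents larger burns and larger treated areas.
- **A reader might infer that allelic reactivity will identify the source.** The documents give neither the donors' HLA types nor the antigens tested, and shared alleles would leave some cases unresolved.

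**Conclusion.** The point holds as a limitation of the planned summary. One crude percentage per visit, in a study without a control arm, cannot separate product-related antibody from antibody related to transfusion or human allograft. Nor does it separate new antibody from antibody present at Day 1.

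This conclusion rests on the text of SAP 3.9.5 and on the general premise that blood and human allograft carry foreign HLA. It does not depend on the assumed rates. Those rates show only that the ambiguity could be material, and no magnitude beyond that illustration can be stated. The primary endpoint is unaffected. The change is worth making before database lock because it uses data already due to be collected.

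**What to change.** Amend SAP 3.9.5 as follows.

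1. Among subjects with a negative Day 1 result for the class concerned, tabulate new class I positivity and new class II positivity separately at Week 4 and Week 12, with denominators shown.
2. Present each overall and split by whether a transfusion or human allograft was recorded before that sample. Define exposure from the concomitant procedure records. For exposure before consent, also use the acute burn and medical history, after checking that those forms capture it.
3. Describe the unexposed stratum as the least confounded descriptive estimate, not as the sole basis for conclusions, and state its likely selection towards smaller burns and treated areas. Use exact intervals if intervals are shown, because the normal approximation in SAP 3.1 has zero width when no subject converts.
4. If the sponsor holds the HLA types of the two product cell donors, summarise the allelic-reactivity results already planned as donor-matching or non-matching specificities, with a note that shared alleles may leave cases unresolved.

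The cost is SAP wording and one or two extra tables, with no new samples. The drawback is smaller groups and wider uncertainty in each stratum.

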Study Design: This is a prospective, open-label, single-arm study assessing the safety and clinical outcomes of StrataGraft skin tissue in the treatment of DPT thermal burn injuries with intact dermal elements. Study enrollment will be approximately 100 subjects but will continue until StrataGraft becomes commercially available or until the Sponsor decides to close the study. Enrollment will include subjects with a minimum of 3% and up to 50% TBSA of partial +/- full thickness thermal burn. Treatment will include a single application of up to 1:1 meshed StrataGraft skin tissue on DPT wound(s) totaling no more than approximately 2000 square centimeters in area (no more than 3 study treatment thermal burn areas and no more than 20 StrataGraft tissues applied to the study treatment areas). The wound bed must be clean, excised and have bleeding controlled prior to StrataGraft tissue application. The tissues may be anchored with tissue adhesive, staples, or sutures, covered with a nonadherent, nonocclusive contact layer and additional secondary dressings per institutional standard of care (dressings should not contain silver). Safety assessments will include monitoring of TEAEs, serious adverse events (SAEs), wound infections, and clinically significant vital signs, laboratory test results, and immunological changes. Wound assessments will include measurements for average depth, length, and width for calculations of area and percent epithelialization. Wound assessments will be facilitated by photographs taken by the subject and/or taken by the clinical study site staff at study visits throughout the study. Scar evaluation using the POSAS will be conducted. Additionally, HCRU data will be collected. All subjects eligible to be consented throughout the duration of the study following application of StrataGraft skin tissue to be part of a contact database and follow-up registry; subjects will have the choice to decline with no impact to their participation in the study. In addition, a subset of 10 subjects (sourced from across all the sites) with closed wounds will be separately consented to have a punch biopsy (measuring 3 mm) taken from the center of the healed burn wound, and another punch biopsy measuring 3 mm taken from non-burned healthy skin. A histological evaluation of both samples will be done to analyze and contrast the skin architecture in the healed burn wound with healthy skin. The biopsy will happen at the study visit Week 12, regardless of when wound closure occurs.

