12.2.3. Immunology

Blood collection for PRA testing (HLA I and II) will be conducted at Day 1 (Baseline), Week 4, and Week 12.

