3.1.2 Date/Time Derived Variable Conventions

Study Day 1 (application of StrataGraft) will be considered as baseline for the endpoint calculation. If the value is not available at Study Day 1, the last available observed value prior to application of StrataGraft will be used.

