3.9.2 Laboratory Assessments

Hematology and biochemistry will be collected at baseline (Day 1 or possibly within 48 hours of surgery) and Week 12. Summaries of baseline assessment and change from baseline for laboratory assessments will be summarized by number of subjects, mean, standard deviation, median, minimum and maximum.

Hematology and biochemistry laboratory results will be classified as status of 'Low', 'Normal' and 'High' as defined by central lab', and in some cases, by the sites' laboratory normal range. Shift tables summarizing status of changes from baseline at Week 12 according to baseline status will be provided for subjects with both baseline and Week 12 results.

Hematology and biochemistry parameters will be categorized as normal, non-clinical significance and clinical significance at Baseline and Week 12 by the clinician according to the institutional SoC in the evaluation of study subjects. Shift tables of change from baseline to Week 12 will be created for laboratory results using clinically significant categories.

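### SAP 3.9.5 reports HLA antibody positivity only visit by visit, so the number of baseline-negative subjects who become positive after StrataGraft is not quantified

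*SAP*

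**What the plan says.** Protocol 12.2.3 sets the sampling: "Blood collection for PRA testing (HLA I and II) will be conducted at Day 1 (Baseline), Week 4, and Week 12". SAP 3.9.5 repeats it as "screening and testing for allelic reactivity at Day 1, Week 4 and Week 12" and then gives one summary: "The number (%) of subjects that are HLA Class I and II positive will be provided for each visit". Protocol 12.3.5.3 names the tests but no analysis, and Protocol 13.3.7 (Safety Analysis) does not mention immunology. Neither document plans a change-from-baseline, shift or new-onset summary for these results.

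Four other parts of the plan bear on this:

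- **Aim.** The protocol synopsis lists among the monitored safety items "clinically significant vital signs, laboratory test results, and immunological changes". The amendment history says PRA testing was added to supplement the development programme's data "by providing additional HLA I and II findings associated with the use of StrataGraft skin tissue".
- **Baseline.** SAP 3.1.2 says: "Study Day 1 (application of StrataGraft) will be considered as baseline for the endpoint calculation".
- **Other laboratory data.** For hematology and biochemistry, SAP 3.9.2 says: "Shift tables summarizing status of changes from baseline at Week 12 according to baseline status will be provided". Those tables are limited to subjects with both results.
- **Missing data.** SAP 3.1.1 uses observed values with no imputation.

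The exclusion criteria (Protocol 7.2) do not remove subjects with existing HLA antibodies, so some may be positive on Day 1.

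**The concern.** For an allogeneic tissue, the natural question of an antibody test repeated after application is how many subjects without antibodies acquired them. That is a within-subject question. A percentage positive per visit is a marginal summary. It combines subjects positive from the start with those newly positive, and a new positive can be offset by a baseline positive who reverts or has no later sample. The percentage can also rise with nobody converting, if the missing samples come mainly from negative subjects.

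At stake is whether the study report can give a pre-specified statement on new HLA antibodies. As planned, it could report prevalence at three times, and a reader would have to work out conversions from the listings. The plan already uses paired tables for routine hematology and biochemistry, yet the test most specific to an allogeneic product has none.

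**Working it through.** The plan gives no PRA figure to reproduce: no expected positivity, conversion rate or precision target. What can be checked is how far the planned summary determines the number of conversions.

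**Inputs.** From the documents: about 100 subjects (SAP 2.3), samples at Day 1, Week 4 and Week 12, and observed values only (SAP 3.1.1). Assumed, because the documents give nothing: every positivity rate and the number of missing Week 12 samples below.

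**1. Everyone sampled.** Let *b* be the number positive on Day 1, *w* the number positive at Week 12, and N = 100. New conversions lie between max(0, *w* − *b*) and min(*w*, N − *b*).

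- *b* = 20, *w* = 20: 0 to 20 conversions, that is 0/80 = 0% to 20/80 = 25% of baseline-negative subjects.
- *b* = 20, *w* = 25: 5 to 25 conversions, 5/80 = 6.25% to 25/80 = 31.25%.

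If prevalence does not change, the upper bound depends on the assumed baseline rate: 5/95 = 5.3% at 5% positive, 10/90 = 11.1% at 10%, 30/70 = 42.9% at 30% and 40/60 = 66.7% at 40%. With complete sampling, the upper bound is reached only if every baseline positive reverts.

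**2. Some Week 12 samples missing.** Assume 15/100 positive on Day 1 and 16/80 at Week 12. Let *d* be the baseline positives without a Week 12 sample and *r* the tested baseline positives who revert. Then:

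- baseline-negative subjects tested at Week 12 = 80 − (15 − *d*) = 65 + *d*;
- conversions = 16 − (15 − *d* − *r*) = 1 + *d* + *r*.

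| Case | *d* | *r* | Conversions / baseline-negatives tested |
|---|---|---|---|
| No positives lost, none revert | 0 | 0 | 1/65 = 1.5% |
| Loss in proportion (15 × 20/100 = 3) | 3 | 0 | 4/68 = 5.9% |
| All positives lack a Week 12 sample | 15 | 0 | 16/80 = 20% |
| All positives tested and all revert | 0 | 15 | 16/65 = 24.6% |

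The planned table shows 15% and 20% in all four cases.

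**3. Missing samples alone.** Assume 20/100 positive on Day 1, 20 subjects without a Week 12 sample and no change of status in anyone. The Week 12 figure is 20/80 = 25% if all 20 were negative, (20 − 4)/80 = 20% if 4 of them were positive (loss in proportion), and 0/80 = 0% if all were positive.

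**4. What a paired table would give.** With 80 baseline-negative subjects tested (assumed), 5 new positives would be 5/80 = 6.25%, exact 95% CI 2.1% to 14.0%. None would be 0/80, with upper limit 1 − 0.025^(1/80) = 4.5%. With all 100 subjects sampled and assumed baseline positivity from 5% to 40% (95 to 60 at risk), the upper limit for zero conversions runs from 3.8% to 6.0%.

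**The case against.** Several points on the other side stand.

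- **Net change is visible.** A reader might infer that the table cannot show sensitisation at all, or that the Day 1 sample is ignored. Neither is so: Day 1 is one of the displayed visits, and with complete sampling a net rise is a lower bound on new positives. What is missing is the within-subject link.
- **The denominator is not stated.** SAP 3.9.5 gives none. That it changes between visits is an inference from SAP 3.1.1, though a reasonable one.
- **The classes may not be pooled.** The phrase on class I and II could mean each, either or both. The protocol uses similar shorthand for the two tests, so this is an ambiguity to settle, not evidence of pooling.
- **Other allogeneic exposures are used.** Protocol 8.3 records concomitant procedures, "including transfusions, use of xenogenic or allogeneic products", and SAP 3.6 summarises them. They are simply not linked to the PRA results. Splitting the PRA table by them would be sparse in about 100 subjects. Recording starts at consent, and a split on exposure since Day 1 would count earlier exposure as none.
- **The consequence is limited.** PRA is not a primary, other or exploratory endpoint, all analyses are descriptive, and the planned listings (Protocol 13.3, SAP 3.1) allow conversions to be found by hand. The table shells and programming specifications are separate documents and may contain more.

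These points limit the claim but do not remove it. Listings and unseen shells do not replace a summary stated in the SAP, whose own purpose is to pre-specify the analyses.

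**Conclusion.** The point holds in this form: the planned summary gives net prevalence per visit and does not quantify new positivity among baseline-negative subjects. In the assumed example with missing samples, the same two percentages fit a conversion rate from 1.5% to 24.6%. The upper end needs every baseline positive to revert, and 20% needs every one of them to lack a Week 12 sample. Nothing in the documents suggests either. Loss in proportion without reversion gives 5.9%. The range shows what the table leaves open; it does not predict a result.

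A reader might go further and take a paired table as evidence that StrataGraft causes sensitisation. The design does not support that: there is one arm, and transfusions and allogeneic products are possible concomitant exposures. The paired result would describe sensitisation after application only.

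**What to change.** Add to SAP 3.9.5, in line with the shift tables in SAP 3.9.2:

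- tables of Day 1 status against Week 4 and against Week 12, for class I and class II separately, in subjects with results at both times;
- as the main figure, n/N (%) of baseline-negative subjects who become positive, with an exact (Clopper-Pearson) 95% CI. The method should be named, because the default in SAP 3.1 is the normal approximation, which at 0/80 gives an interval of zero width;
- the positivity cut-off used, which neither document states;
- a listing of the converters with any recorded transfusion or allogeneic product, in place of a split of the table;
- the per-visit prevalence, kept as a secondary display with its denominator shown;
- a sentence saying that the result is not attributable to StrataGraft alone.

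The cost is four small tables (two classes by two follow-up times) and one listing. No new samples, visits or subjects are needed, so this is a free improvement.
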